Patients with compensated cirrhosis are substaged based on the severity of portal hypertension (Figure 1).⁹ However, measurement of portal pressure through direct puncture of the portal vein is risky and not routinely performed. Therefore, portal pressure is assessed indirectly by calculation of hepatic vein pressure gradient (HVPG) by measuring the difference between wedge and free hepatic venous pressure.¹⁰⁻¹² The normal value of HVPG is between 3 and 5 mmHg.^{11, 12} Currently, the severity of portal hypertension is defined as mild when HVPG is ≥ 6 but <10 mm Hg, ≥ 10 mm Hg as clinically significant portal hypertension (CSPH), and ≥ 12 mm Hg as severe portal hypertension (SPH).¹³ Evaluation of a compensated cirrhotic by HVPG is ideal for risk stratification as CSPH is associated with an increased risk of varices, decompensation (ascites, variceal hemorrhage and/or hepatic encephalopathy) and hepatocellular cancer.¹⁴⁻¹⁶ However, measurement of HVPG is cumbersome, invasive, non-standardized and often limited to tertiary care centers due to limited expertise.¹⁷ Therefore, there is a need for non-invasive tools that can estimate HVPG easily, reproducibly and with high diagnostic accuracy. It is thus not a surprise that some investigators have examined the prognostic value of AST-to-Platelets Ratio Index (APRI) and fibrosis-4 (FIB-4) for prediction of adverse clinical outcomes related to portal hypertension.^{18, 19}

Liver stiffness measurement (LSM) by vibration controlled transient elastography (VCTE) is currently used for non-invasive diagnosis liver fibrosis in patients with chronic liver disease. In patients with cirrhosis, LSM is likely indicative of cumulative stiffness from underlying liver fibrosis and portal hypertension. In addition, some studies have reported a good correlation between LSM and HVPG and its ability to detect CSPH.^{20, 21} In fact, in the recent Baveno conference (Baveno VI), a screening endoscopy was not recommended in patients with LSM <20 kilopascals (kPa) and platelet count $>150,000/\mu\text{l}$ due to very low risk of having varices at high risk of bleeding.^{21, 22} In one study that examined the prognostic accuracy of HVPG and serum fibrosis biomarkers, both measures worked equally well in predicting clinical outcomes.¹⁹

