Specific Aim 1: To examine the relationship between LSM by Velacur and the presence of esophageal or gastric varices and portal hypertensive gastropathy in patients with compensated

advanced chronic liver disease (cACLD). We will measure LSM by Velacur in this single center clinical study comprising of 200 patients with cACLD (defined by LSM ≥ 10 kilopascals (kPa) according to the Baveno VI recommendations) who have not had a liver transplant.

Specific Aim 2: Compare the performance of LSM by Velacur for predicting CSPH, esophageal and gastric varices to that of FibroScan® and other non-invasive markers such as MELD, CPT, platelets count, splenomegaly, APRI and FIB4.

Proposed Study Design: This is a cross sectional study that evaluates the relationship between LSM by Velacur in patients with cACLD and manifestations of portal hypertension.

Inclusion/Exclusion Criteria

Inclusion criteria:

1. Adults aged 18 years or older
2. Ability to provide informed consent
3. Diagnosis of cirrhosis based on liver biopsy, imaging, FibroScan®, or Hepatologist assessment.
4. Planned or recommendation of one of the following:
 - a. standard of care upper endoscopy to screen for varices within (+/-) 6 months of the Velacur study
 - b. standard of care transjugular liver biopsy with portal pressure measurement within (+/-) 6 months of the Velacur study

Exclusion criteria:

1. Inability or refusal to provide informed consent
2. Fasting for less than three hours prior to the scan
3. Subject is a pregnant or lactating female
4. Current, significant alcohol consumption
5. Subject is unable to reliably quantify alcohol consumption based upon local study physician judgment
6. Patients with a pacemaker or defibrillator
7. Acute hepatitis defined as AST/ALT > 500 U/L
8. Ascites

Screening and Enrollment

Up to 200 patients with cACLD who have not undergone liver transplantation who are seen in the liver clinics at IUH-Digestive and Liver Disorder Clinics and at Springmill Clinic will be enrolled into this prospective cross sectional study after obtaining informed consent. Standard inclusion and exclusion criteria for Velacur will be used. Patients who meet the inclusion criteria will be offered the opportunity to undergo additional testing with Velacur to measure LSM after informed consent. In addition to history and physical, we will capture pre-specified liver related findings using standardized case report forms. Participants will be enrolled over a 24 month period.

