Study Procedures

At Enrollment: After subject identification, an informed consent will be obtained. All patients have to be fasting for at least three hours prior to performance of the study. Velacur exam will be performed by a Velacur certified technician. Duration of participation for the subject should be no more than one hour. Medical information from the subjects, including results of the scans, historical laboratory and diagnostic testing data will be obtained from medical records and will be entered into a database. Laboratory data for calculating non-invasive markers such as MELD, CPT, platelets count, splenomegaly, APRI and FIB4 will be collected from standard of care labs done within 6 months of the endoscopy or portal pressure measurement by transjugular liver biopsy.

Reporting of Adverse Events or Unanticipated Problems Involving Risk to Participants or Others

The Division of Gastroenterology/Hepatology at IUSM has considerable experience in the conduct of clinical studies.

Participation in this study may cause a loss of privacy. To minimize this risk, all of the patient's personal and medical data will be considered confidential to the extent allowed by law; every effort will be made to keep all of the information strictly confidential. All study information will be stored in locked cabinets and on password-protected computers. Only authorized personnel will have

access to the samples, databases, and results. When the study is published, no names or other identifying information will be used.

While there are no direct risks from use of Velacur, patients may be uncomfortable lying on their back for a brief period of time. They may experience soreness at the probe site. There is a small risk of an allergic reaction to the gel utilized during the procedure.

Patients will be closely monitored for any evidence of adverse events. Any adverse events associated with the study will be documented and the IRB will be notified per reporting guidelines.

Study Withdrawal/Discontinuation

The subject is free to withdraw from the study for any reason and at any time without giving a reason for doing so and without penalty or prejudice. The Investigator is also free to terminate a subject's involvement in the study at any time if the subject's clinical condition warrants it.

Statistical Considerations

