Descriptive statistics such as mean, standard error, and percentages were used to characterize the cohort. Comparisons will be made between groups by using Student t test or analysis of variance. Pearson correlation coefficient will be used to detect the correlation between continuous variables. Multivariate analysis will be performed to examine the independent association between dependent and several independent variables. The diagnostic accuracy of LSM will be calculated using area under the receiver operator curve analysis. Sample size is based on clinical experience and precedent established for studies of similar design.

Privacy/Confidentiality Issues

Participation in this study may cause a loss of privacy. To minimize this risk, all of the patient's personal and medical data will be considered confidential to the extent allowed by law; every effort will be made to keep all of the information strictly confidential. All study information will be stored in locked cabinets and on password-protected computers. Only authorized personnel will have access to the samples, databases, and results. Samples will be labeled with a code. When the study is published, no names or other identifying information will be used.

Follow-up and Record Retention

Use of Velacur is an additional tool for diagnostic purposes and provides physicians with additional clinical information to optimize patient care. No direct follow-up with participants is planned. However, the patients may be approached for repeat study and with informed consent may be enrolled again to measure any changes in the LSM and SS that may occur over time. Study records and documents will be maintained in accordance with federal, state, and university laws.

References:

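### Nothing in the plan keeps the Velacur result from being known before the reference test is done or read, so the index test may influence its own reference

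*Protocol*

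**What the plan says.** **Use of the result.** Under Follow-up and Record Retention the protocol says: "Use of Velacur is an additional tool for diagnostic purposes and provides physicians with additional clinical information to optimize patient care". No timing and no recipient beyond physicians in general is given.

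**Status and timing of the reference.** Inclusion criterion 4 asks for "Planned or recommendation of one of the following": "standard of care upper endoscopy to screen for varices within (+/-) 6 months of the Velacur study", or "standard of care transjugular liver biopsy with portal pressure measurement within (+/-) 6 months of the Velacur study". Entry does not require the procedure to have been done, and it may fall on either side of the scan.

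**Source of the data.** Under Study Procedures, "historical laboratory and diagnostic testing data will be obtained from medical records and will be entered into a database". No masked or central reading of endoscopy is described. The follow-up section adds: "No direct follow-up with participants is planned".

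**Stiffness and the decision to scope.** The Introduction cites a consensus conference under which "a screening endoscopy was not recommended in patients with LSM <20 kilopascals (kPa) and platelet count" above 150,000/µl. That paragraph concerns stiffness by transient elastography (VCTE).

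**Analysis.** The Statistical Considerations, identical in protocol and SAP, name the area under the ROC curve as the accuracy measure. They are silent on masking, test order and patients without a reference result.

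**The concern.** An accuracy estimate is sound only if the reference is obtained and read independently of the index test. This plan leaves three routes open.

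- **Completion (scanned first).** A stiffness value that reaches the physician may affect whether a recommended endoscopy goes ahead. Patients with low values would then be under-represented among those with a reference result.
- **Reading (scanned first).** Varices and portal hypertensive gastropathy, both Aim 1 outcomes, are visual calls. An endoscopist who knows the stiffness value may lean towards it. A measured pressure gradient is much less exposed.
- **Acquisition (scanned second).** Nothing masks the Velacur technician to an endoscopy or pressure report already on file.

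Aim 2 is also at stake. Reading bias towards Velacur credits Velacur more than the markers it is compared with, so a spurious advantage could appear.

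**Working it through.** The documents give no figure to reproduce: there is no expected AUC, prevalence, completion rate or share scanned first. What follows is illustration under stated assumptions.

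**Assumed inputs.** Prevalence 0.30. Binormal stiffness with true AUC 0.80, so the mean separation is √2·Φ⁻¹(0.80) = 1.190. A cut at the overall median stiffness gives true sensitivity 0.804 and specificity 0.631. Check: 0.30 × 0.804 + 0.70 × (1 − 0.631) = 0.50.

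**1. Reading bias.** In a fraction f of patients the reference call is replaced by whether stiffness exceeds its 70th percentile, which keeps prevalence at 30%. If only a share s is scanned first, the effective fraction is s × f. By simulation:

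| f among those scanned first | AUC, all scanned first | AUC, half scanned first |
|---|---|---|
| 0 | 0.80 | 0.80 |
| 0.05 | 0.81 | 0.805 |
| 0.10 | 0.82 | 0.81 |
| 0.20 | 0.84 | 0.82 |

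The rise is close to 0.20 × s × f. With a true AUC of 0.75 and all scanned first, the values are 0.76, 0.78 and 0.80.

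**2. Stiffness-dependent completion.** Let v₊ = 0.95 be the completion rate above the median and v₋ the rate below it. Then

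- apparent sensitivity = Se·v₊ / [Se·v₊ + (1 − Se)·v₋]
- apparent specificity = Sp·v₋ / [Sp·v₋ + (1 − Sp)·v₊]

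For v₋ = 0.50: sensitivity = 0.764 / (0.764 + 0.098) = 0.89, and specificity = 0.316 / (0.316 + 0.351) = 0.47.

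| v₋ | Sensitivity (true 0.80) | Specificity (true 0.63) | AUC (true 0.80) |
|---|---|---|---|
| 0.85 | 0.82 | 0.60 | 0.798 |
| 0.70 | 0.85 | 0.56 | 0.794 |
| 0.50 | 0.89 | 0.47 | 0.785 |

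The largest AUC loss is 0.80 − 0.785 = 0.015. If only half the patients are exposed and the rest are completed at 95%, the worst row becomes v₋ = 0.5 × 0.95 + 0.5 × 0.50 = 0.725. This gives sensitivity 0.764 / (0.764 + 0.142) = 0.84 and specificity 0.457 / (0.457 + 0.351) = 0.57.

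A second set-up shows the same pattern. With true sensitivity 0.80, specificity 0.70 and all index-positives verified, verifying 90%, 75% or 50% of index-negatives gives apparent sensitivity 0.82, 0.84 or 0.89 and specificity 0.68, 0.64 or 0.54. The AUC stays at 0.80, 0.80 or 0.79.

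**3. Against sampling error.** With 200 verified patients at 30% prevalence (60 with the outcome, 140 without), the Hanley–McNeil variance is [A(1 − A) + 59(a − A²) + 139(b − A²)] / (60 × 140). Here A = 0.80, a = A/(2 − A) = 0.667 and b = 2A²/(1 + A) = 0.711. This gives (0.160 + 1.573 + 9.884) / 8400 = 0.00138, a standard error of 0.037.

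**4. Aim 2.** Take two markers with true AUC 0.80 and within-group correlation 0.5. If 10–20% of calls follow Velacur alone, with all scanned first, Velacur gains about 0.02–0.04 over its comparator. At correlation 0.8 the gain is about 0.01–0.02. It is smaller if readers also know the FibroScan value.

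**The case against.** A reader might infer that the protocol sends Velacur results to treating physicians while endoscopy is pending. The documents do not say so. The sentence under Follow-up and Record Retention is a general statement about the tool, with no time of release and no mention of the endoscopist or pressure operator. What can be said is that the result is described as serving care and that no rule prevents early disclosure. The technician route rests on silence alone. The limit of access to authorized personnel does not settle the matter either way, because it is a privacy provision.

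A reader might also take the Introduction to show that a low Velacur value cancels endoscopy. The cited rule concerns VCTE stiffness and also requires a platelet count. FibroScan is one permitted basis for diagnosis under criterion 3, so a stiffness value may already be known when the procedure is recommended. The added influence of Velacur is plausible but not shown.

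The numerical objection is fair too. AUC is the only accuracy measure named, incomplete verification hardly moves it, and the half-exposed reading-bias shifts of 0.005–0.02 lie below the standard error of 0.037. The larger shifts are in cut-off measures that neither document plans to report.

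These objections limit the size and certainty of the point but do not remove it. Bias does not shrink as patients are added, a device proposed for risk stratification will eventually need a cut-off, and Aim 2 compares markers whose true differences may be just as small.

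**Conclusion.** The point holds as a gap in conduct and analysis: release timing, masking, completion of the reference and handling of unverified patients are all unspecified, and the plan followed exactly can produce a biased accuracy estimate. It does not hold as a claim that early disclosure is mandated or that bias has occurred.

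The net size and direction cannot be derived. Reading bias raises the AUC and incomplete verification slightly lowers it. Every figure above rests on assumed prevalence, AUC, override and completion rates, and on the unknown share scanned first. The exposure is mainly in endoscopic calls. The change is worth making because it is cheap, and because test order and reader awareness are best recorded prospectively.

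**What to change.** **Preferred: a data-handling rule.** Hold the Velacur stiffness value in the study database and release it to the treating physician and proceduralist only after the reference procedure is reported. Where the procedure came first, the technician records the stiffness value before opening its report. No added patients, visits or procedures are needed. The cost is later access to an add-on result.

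**If release cannot be delayed:**

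- Record test order, whether the reader knew the stiffness value, and the reason for any missing reference.
- Report the AUC by test order as a sensitivity analysis. Neither stratum is clean, because the scanned-second group may have an unmasked technician.
- Correct for incomplete verification with inverse-probability weights, or Begg–Greenes, based on Velacur stiffness, platelet count and other collected markers such as FibroScan. Stiffness alone is not enough if platelets also drive omission. In an illustrative check with 40% completion among patients with low stiffness and high platelets, stiffness-only weights gave sensitivity 0.775 against a true 0.805, and weights using both gave 0.804.
- Report failed scans separately, since such patients have no stiffness value to weight on.

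This costs a few data fields and one added analysis. It addresses verification bias only; it does not remove reading bias.

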Protocol title: Non-invasive Evaluation of Portal Hypertension in Patients With Compensated Advanced Chronic Liver Disease by Liver Stiffness Measurement Using Liver Incytes

PI: [name]

NCT04576897

Statistical Considerations

Document Date: August 5, 2021

Statistical Considerations

Descriptive statistics such as mean, standard error, and percentages were used to characterize the cohort. Comparisons will be made between groups by using Student t test or analysis of variance. Pearson correlation coefficient will be used to detect the correlation between continuous variables. Multivariate analysis will be performed to examine the independent association between dependent and several independent variables. The diagnostic accuracy of LSM will be calculated using area under the receiver operator curve analysis. Sample size is based on clinical experience and precedent established for studies of similar design.
